1.1 SYNOPSIS

1.1 31101313			
Protocol number	LevoDesa_05-2017		
EudraCT number	2018-001149-15		
Title of the Study	Aqueous humour concentrations after topical apPlication of combinEd levofloxacin-dexamethasone eye dRops and of its single components: a randoMized, assEssor-blinded, parallel-group study in patients undergoing cataract surgery - iPERME		
Phase	II		
Sponsor	NTC S.r.l.		
Investigational Sites	 [name]: U.O. Oculistica Universitaria – Azienda Ospedaliera Universitaria Pisana – Presidio Ospedaliero di Cisanello – Pisa [name]: Clinica Oculistica – Presidio Ospedale San Paolo – Milan 		
Study Objective	To evaluate the penetration of levofloxacin and dexamethasone 21-phosphate into the aqueous humour after ocular administration in combination or as single active ingredients.		
Study Endpoint	Aqueous humour concentration of levofloxacin, dexamethasone 21-phosphate and dexamethasone.		
Type of Study	This is a randomized, assessor-blinded, parallel-group study.		
Number of Patients	The study will enrol 120 patients scheduled for cataract surgery.		
Inclusion Criteria	 Written informed consent must be obtained before any assessment is performed Male or female patients, aged ≥40 years Patient undergoing phacoemulsification Corneal thickness between 450 μm and 600 μm as measured by means of pachymetry 		

	5. Corneal integrity confirmed by means of fluorescein test
	(Oxford scheme grade 0)
	6. Adequate pupil dilation assessed at screening
	7. Female patients of childbearing potential must have a negative
	pregnancy test
	8. Ability to fully understand all study procedures
Exclusion Criteria	1. Corneal epithelium integrity not confirmed by fluorescein test
	2. History of corneal disease or dystrophy (e.g. ocular herpes, conjunctivitis, keratitis)
	3. History of ocular trauma with corneal damage
	4. History of acute ocular inflammation (including uveitis) in the 6
	months prior to screening
	5. Previous ocular surgery (including laser treatment)
	6. Glaucoma
	7. Treatment with an ophthalmic investigational drug in the 3 months prior to screening
	8. Treatment with any topical ocular drug within 12 hours before
	start of cataract surgery other than study drugs and instillation of topical anaesthetic (oxybuprocaine hydrochloride - Novesina®) followed by povidone-iodine (Oftasteril®) within 10
	minutes before start of surgery Or Treatment with any topical startid or antihictic drug in the 7
	9. Treatment with any topical steroid or antibiotic drug in the 7 days prior to cataract surgery (artificial tears without BAK are allowed)
	10. Treatment with any systemic steroid or antibiotic drug in the 7 days prior to cataract surgery
	11. Known hypersensitivity to levofloxacin or other fluoroquinolones and/or dexamethasone or other steroids
	12. Pregnant or lactating women
	13. Patients who have received any investigational drug during the preceding 30 days or 5 times the plasma half-life, whichever is
	longer, or who have previously participated in this trial
	Levofloxacin hemihydrate 5.12 mg/ml, corresponding to 5
Study Drugs	mg/ml levofloxacin + dexamethasone 21-phosphate 1.32 mg/ml, corresponding to dexamethasone 1 mg/ml: two 30 μl
	doses 30 minutes apart.
	• Levofloxacin hemihydrate 5.12 mg/ml (Oftaquix®),
	corresponding to 5 mg/ml levofloxacin: two 30 µl doses 30
	minutes apart.
	• Dexamethasone 21-phosphate 1,50 mg/ml (Tamesad®), corresponding to dexamethasone 1.14 mg/ml: two 26 μl doses
	30 minutes apart.

Study Procedures

After providing informed consent, patients scheduled for cataract surgery will undergo screening assessments to verify eligibility for the study. Screening must not take place more than 28 days prior to surgery.

Eligible patients will be randomly assigned to levofloxacin 5 mg/ml + dexamethasone 1 mg/ml (eye drops, test drug), or to levofloxacin (Oftaquix®) or to dexamethasone (Tamesad®) in a 1:1:1 ratio.

Administration of study drugs will be performed by qualified health care personnel using a micropipette and dispenser. Two doses of one of the study treatments will be administered, the first 90 ± 15 minutes prior to surgery, and the second 60 ± 15 minutes before surgery. The two doses must be administered 30 minutes apart. Doses are to be administered at the lateral canthus while applying pressure at the medial canthus to prevent drainage of the drug.

Before cataract surgery, a limbal paracentesis will be performed and an aqueous humour sample of approximately 0.05 ml will be drawn from the anterior chamber with a 30-gauge needle insulin syringe. The aqueous humour will be stored immediately in vials at -80 °C and subsequently analysed at a central laboratory. Vial labels will contain the kit number but no information regarding the drug received. Laboratory analysts will thus be blinded to the drug administered and samples will be analysed for the concentration of all three molecules (levofloxacin, dexamethasone 21-phosphate and dexamethasone) by means of LC-MS-MS.

Following surgery, patients will be treated with antibiotics and/or steroids according to local clinical practice.

Sample size calculation

[figure not shown]
The study plans to enrol 120 patients: 40 will be assigned to the dexamethasone group, 40 to the levofloxacin group and 40 to the dexamethasone-levofloxacin combination.

The sample size has been estimated based on the expected precision (i.e. width of the 95% confidence interval) of the estimates of the study drug concentrations.

Assessment of dexamethasone concentration: When the sample size is 40, a two-sided 95% confidence interval for a single mean will extend 4.648 ng/ml from the observed mean, assuming that the standard deviation is known to be 15 ng/ml and the confidence interval is based on the large sample z statistic.

	Assessment of levofloxacin concentration: When the sample size is 40, a two-sided 95% confidence interval for a single mean will extend 61.676 ng/ml from the observed mean, assuming that the standard deviation is known to be 199.022 ng/ml and the confidence interval is based on the large sample z statistic.
Drug analysis	All biological samples will be sent to the central laboratory, Ticinumlab, Novara (Italy), which will perform in one run the LC-MS-MS (triple quadrupole) analyses for the simultaneous determination of levofloxacin, dexamethasone and dexamethasone 21-phosphate.
Statistical considerations	Continuous data will be summarized with standard descriptive statistics (i.e. the mean, standard deviation, minimum, median and maximum, 95% confidence limits). Categorical data will be summarized by frequencies and percentages. All analyses will be performed using SAS version 9.4 or later.
Duration of the study	Estimated date of the first visit of the first patient (FPFV): Q2, 2018 Estimated date of the first visit of the last patient (LPFV): Q1, 2019 Estimated date of the last visit of the last patient (LPLV): Q1, 2019
Version and date	V 1.0 – 21 March 2018

1.2 STUDY DESIGN

1.3 SCHEDULE OF ACTIVITIES (SOA)

		Day of surgery			
Procedures	Screeninga	Pre-dose	First dose	Second dose	Limbal
		Pre-dose	-90 (±15) min	-60 (±15) min	Paracentesis
Informed consent	Χ				
Demographics	Χ				
Medical history	Χ				
Concomitant medications	Χ	Χ			
Pachymetry	Χ				
Fluorescein test	Χ				
Inclusion/Exclusion	Х	Х			
criteria	Χ	Α			
Pregnancy test ^b		Χ			
Randomization		Χ			
Study drug administration ^c			Х	X	
Limbal paracentesis					Х
Administration of					Х
Mydrane ^{®d}					^
Adverse event review and	Х	Х	Х	X	Х
evaluation ^e	^	^	^	^	^

^a Screening must take place not more than 28 days prior to surgery.

^b Urine pregnancy test (women of childbearing potential).

 $^{^{\}rm c}$ Two doses 30 minutes apart, the first 90 (\pm 15) minutes prior to surgery, and the second 60 (\pm 15) minutes prior to surgery.

^d Mydrane[®] is to be administered following withdrawal of aqueous humour.

^e Adverse events are to be reported until 7 (for non-serious AEs) or 30 days (for SAEs) after the last day of study participation.

2 INTRODUCTION

2.1 STUDY RATIONALE

In most cases, postoperative care after cataract surgery consists of anti-inflammatory and antibacterial drug therapy. The use of an ophthalmic solution containing the combination of a steroid and an antibiotic is routinely used in clinical practice also because it favours the proper administration of the two agents, reduces the possibility of inaccurate dosage and improves patient compliance with medication. To reduce the emergence of antibiotic resistance, treatment with an antibiotic should however not be longer than the time necessary for the healing of surgically induced epithelial lesions, and therefore should not last more than a week.

Based on these considerations, there is clear interest in having a combination of a broad-spectrum antibiotic with a highly effective corticosteroid that can be used for a short period of time (one week). The combination of dexamethasone and levofloxacin tested in this study is the first combination of a steroid and a quinolone under development and represents a major step forward in the prevention and treatment of post-operative inflammation and prevention of post-operative infections.

Levofloxacin 0.5% – dexamethasone 0.1% ophthalmic solution is an anti-inflammatory/antibiotic combination indicated for the prevention and treatment of inflammation and prevention of infection associated with cataract surgery in adults. The active components of this combination are currently available in marketed ophthalmic products. The purpose of this study is to measure the concentrations of levofloxacin and dexamethasone in the aqueous humour (AH) after topical application of the combined ophthalmic solution and its single components.

2.2 BACKGROUND

Cataract is an ocular condition that causes vision impairment due to changes in the opacity of the ocular lens. Cataract is an age-related condition, but smoking, ocular trauma, exposure to ultraviolet light, diabetes and drug induced metabolic changes in the lens are risk factors for lens opacification causing cataract.¹

The only cure for cataract is surgical, with phacoemulsification with lens implantation as the treatment of choice.² Recovery after surgery is easier than it was in the past and patients usually no longer require in-patient hospital care, with recovery usually uneventful and pain-free. However, adverse events may occur due to corneal trauma, ocular inflammation and dryness, which can result in ocular irritation during the recovery period.³⁻⁵ These conditions may cause symptoms such as pain, burning, stinging, foreign body sensation, itchiness and glare in the operated eye. The incidence of ocular irritation symptoms experienced during the first postoperative hours may be as high as 98%.⁶ Conjunctival hyperaemia, anterior chamber cells and flare and cystoid macular oedema are some possible signs of inflammation after cataract surgery.

In many cases, inflammation is self-limiting, but drug therapy is often used to shorten resolution time and improve ocular comfort.⁷

Steroidal and non-steroidal anti-inflammatory drugs are used to prevent and treat postoperative inflammation. Topical corticosteroids are usually administered for 1 to 6 weeks after cataract surgery. According to the practice pattern studies published by the American Society of Cataract Refractive Surgery (2012), Canadian Ophthalmological Society members study 2011⁸ and European Society of Cataract and Refractive Surgeons (ESCRS), there are variations in postoperative drug therapy provided to individual patients and among different countries. In Europe, dexamethasone was the most commonly used steroidal anti-inflammatory drug and was chosen as the preferred drug by 71% of ophthalmological surgeons.⁹

Endophthalmitis, is a rare yet severe condition that occurs in 0.03–0.3% of patients undergoing cataract surgery. ^{10,11} This condition usually appears during the first days after surgery, and in 80% of cases, endophthalmitis will have developed during the first 6 weeks after surgery. ^{11,12} Topically applied antibiotics are routinely used for the prophylaxis of postoperative bacterial ocular infections such as endophthalmitis. Intraocular, usually intracameral or subconjunctival antibiotics are used during surgery, and both pre- and postoperative topical applications are also provided. ¹⁰ To increase the efficacy of this approach, a broad-spectrum antibiotic should be chosen.

A prospective observational study was conducted to determine the antibiotic susceptibility patterns of conjunctival bacterial flora isolated preoperatively from patients undergoing anterior segment surgery. Of the 120 eyes studied, 21 (18%) showed no bacterial growth. Of the 143 bacterial strains isolated from the remaining 99 eyes, 112 (78%) were coagulase-negative staphylococci (CNS). Among the CNS, greater than 90% were susceptible to cefotaxime, levofloxacin, imipenem, meropenem, vancomycin, and each of the aminoglycosides except neomycin. Between 70% and 90% of the CNS were susceptible to cefazolin, neomycin, ciprofloxacin, ofloxacin, norfloxacin, and chloramphenicol.¹³

Based on these results, quinolones clearly represent a rational approach to the prevention of ocular infections after cataract surgery. Indeed, among available antibiotics for ophthalmic use, quinolones are characterized by a broad spectrum that includes both the Gram-positive and Gramnegative bacteria that are most frequently responsible for ocular bacterial infections.

In most cases, postoperative care after cataract surgery consists of anti-inflammatory and antibacterial drug therapy. Topical anti-inflammatory agents and antibiotics are both routinely provided after cataract surgery. The combined administration of corticosteroids and antibiotics guarantees a powerful anti-inflammatory effect, and contemporarily a preventive/therapeutic action against infections related either to the intensity of the inflammatory process or to the immunosuppressive effect of the steroid.

However, use of such a combination should also be in line with the modern approach to antimicrobial therapy, which advocates preventing increasing bacterial resistance caused by the

Sponsor: NTC S.r.l. Version 1.0

Protocol No.: LevoDesa 05-2017 21 March 2018

inappropriate use of antibiotics. The ESCRS guidelines do not indicate a specific antibiotic to be used for topical postoperative treatment, nor a precise duration of such treatment, although they emphasize the importance of rational use to limit the development of bacterial resistance, especially when a broad-spectrum antibiotic is used. ¹⁴ For this reason, antibiotic treatment should not be prolonged beyond the time necessary for the healing of surgically induced epithelial lesions, and therefore should not last more than a week.¹⁵

In light of these considerations, having the combination of a broad-spectrum antibiotic and a highly effective corticosteroid to be used for a short period of time would be of great clinical interest. The association of dexamethasone 1 mg/ml and levofloxacin 5 mg/ml tested in this study is the first combination of a steroid and a quinolone under development and represents a major step forward in this direction.

The concentration of dexamethasone (1 mg/ml) is well-established in ophthalmic solutions both as sole active ingredient or in combination with an antibiotic to prevent ocular inflammation following cataract surgery. After topical administration of 0.1% solutions of this agent, the concentration in the aqueous humour is adequate to exert its potent anti-inflammatory activity at the site of action. 16 The dexamethasone 21-phosphate salt is freely soluble in water and thus the solution does not require shaking before application and guarantees consistency of the content of the active ingredient at each application.

The pharmacokinetics of both levofloxacin and dexamethasone administered individually confirm that after application as an eye drop solution, both active drugs reach significant concentrations in the aqueous humour, with peaks of aqueous levels between 90 and 150 minutes, and detectable concentrations after 12 hours from dosing. 16-21 Conversely, the concentrations in plasma are negligible, which guarantees lack of systemic effects during a short-course treatment.

The purpose of this study is to analyse the aqueous humour drug concentrations of levofloxacin and dexamethasone administered topically in combination and as single components to assess the penetration of these agents and provide data for clinical use.

RISK/BENEFIT ASSESSMENT

2.3.1 KNOWN POTENTIAL RISKS

In toxicity studies, the only toxicity data reported for dexamethasone were those related to an exaggerated pharmacological activity including a negative feedback on the pituitary-adrenal axis. Systemic effects are however not expected or are negligible when the drug is topically administered as eye drops and for a limited period of time. Nevertheless, its potential effect on foetal development and on newborns suggests it be used very carefully in pregnant women and to discard milk during lactation.^{22,23}

Sponsor: NTC S.r.l.

Version 1.0

Protocol No.: LevoDesa_05-2017 21 March 2018

Possible adverse effects of topical ocular corticosteroid therapy consist of an increase of intraocular pressure (IOP), inhibition of corneal wound healing and increased likelihood of infection and serious complications, but systemic adverse effects are rare.^{7,24}

Levofloxacin is not toxic on reproduction and does not have mutagenic or carcinogenic potential. It is not irritating after eye instillation, but it is phototoxic at very high doses and photosensitization may not be excluded. Thus, it is suggested not to expose patients to direct sunlight during treatment with eye drops containing levofloxacin.

2.3.2 KNOWN POTENTIAL BENEFITS

The efficacy of dexamethasone as anti-inflammatory agent and of levofloxacin as antibiotic in ophthalmology is well established. Combining the two agents would favour their proper administration, reduce the possibility of inaccurate dosage and improve patient compliance. The combination would also allow the implementation of a shorter antibiotic treatment period as compared to other marketed products and thus prevent the emergence of antibiotic resistance.

2.3.3 ASSESSMENT OF POTENTIAL RISKS AND BENEFITS

All things considered, the potential benefits of this trial surely outweigh their potential risks.

3 OBJECTIVES AND ENDPOINTS

OBJECTIVE	ENDPOINT	JUSTIFICATION FOR ENDPOINT
To evaluate the penetration of levofloxacin/dexamethasone 21-phosphate into the aqueous humour after ocular administration in combination or as single active ingredients.	Aqueous humour concentration of levofloxacin and dexamethasone.	The endpoint is standard for penetration studies of ophthalmic preparations into the aqueous humour.

4 STUDY DESIGN

4.1 OVERALL DESIGN

This is a randomized, assessor-blinded, parallel-group clinical study.

One hundred and twenty (120) patients scheduled for cataract surgery at 2 centres who have provided written informed consent will undergo screening procedures during a preoperative visit. Prior to surgery, and once eligibility criteria have been confirmed, eligible patients will be assigned to one of the three following treatment groups in a 1:1:1 ratio:

- Levofloxacin 5 mg/ml + dexamethasone 1 mg/ml (test drug)
- Levofloxacin (Oftaquix®)

• Dexamethasone (Tamesad®)

Administration of study drugs will be performed by qualified health care personnel using a micropipette and dispenser. Two doses of one of the study treatments will be administered, the first 90 ± 15 minutes prior to surgery, and the second 60 ± 15 minutes before surgery. The two doses must be administered 30 minutes apart. Eye drops are to be administered at the lateral canthus while applying pressure at the medial canthus to prevent drainage of the drug.

Phacoemulsification and limbal paracentesis will be performed by an experienced surgeon. Before the main incisions of phacoemulsification, approximately 0.05 ml of aqueous humour will be drawn from the anterior chamber with a 30-gauge needle syringe. Mydrane[®], a combined solution (phenylephrine [0.31%], tropicamide [0.02%] and lidocaine [1%]) for intracameral injection indicated for cataract surgery to obtain mydriasis and intraocular anaesthesia during the surgical procedure is to be administered following paracentesis. The patient's participation in the study will end with the administration of Mydrane[®]. Following surgery, patients will be treated with antibiotics and/or steroids according to local clinical practice.

The aqueous humour will be stored immediately in vials at -80°C and subsequently analysed at a central laboratory. Vial labels will contain the study kit number but no information regarding the drug received. The laboratory analyst will be blinded to the drug administered and samples will be analysed for the concentration of all three molecules (levofloxacin, dexamethasone 21-phosphate and dexamethasone) by means of an LC tandem mass spectrometry method. Quality control samples blinded to the analyst will be included following advice from BfArM. To that end, the randomization list will include kit numbers corresponding to quality control samples. A different analyst will prepare twelve samples (4 of each active principle) with synthetic aqueous humour and a known concentration of the active ingredients in pre-labelled vials at the central laboratory in the presence of personnel belonging to a Contract Research Organization (CRO) (OPIS s.r.l.) working on behalf of the Sponsor. The twelve quality control samples correspond to 10% of the true biological samples obtained from the patients.

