4.2 SCIENTIFIC RATIONALE FOR STUDY DESIGN

The randomized design is standard for studies investigating the penetration of ophthalmic preparations into the aqueous humour. The laboratory analyst will be blinded to the drug administered to ensure an unbiased analysis (see *Section 4.1*).

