6.3 MEASURES TO MINIMIZE BIAS: RANDOMIZATION AND BLINDING

Patients will be randomized to one of the three treatment groups described in the sections above in a 1:1:1 ratio. Randomization is stratified by centre.

The randomization numbers will be generated using procedures that ensure that treatment assignment is unbiased. A patient randomization list will be produced using a validated system that automates the random assignment of patient numbers to randomization numbers.

Prior to surgery, patients who fulfil all inclusion criteria and none of the exclusion criteria will be randomized via an Interactive Web Response System (IWRS) that will assign the patient a randomization number linked to a treatment arm.

Vials containing frozen humour aqueous samples will be labelled and shipped to a centralized laboratory for analysis. Vial labels will contain the kit numbers but no information regarding the drug received. Laboratory analysts will thus be blinded to the drug administered and samples will be analysed for the concentration of all three molecules (levofloxacin, dexamethasone 21-phosphate and dexamethasone. Quality control samples blinded to the analyst will be included. To that end, the randomization list will include kit numbers corresponding to quality control samples. Twelve samples (4 of each active principle) will be prepared with synthetic aqueous humour and a known concentration of the active ingredients in pre-labelled vials at the central laboratory by a different analyst in presence of OPIS personnel.

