8.2 LABORATORY ANALYSES

The concentration of levofloxacin, dexamethasone 21-phosphate and dexamethasone will be measured by LC tandem mass spectrometry at the centralised laboratory Ticinumlab (Novara, Italy). Ticinumlab is a laboratory working according to Good Laboratory Practice (GLP) and qualified by the Health Authority for the analysis of biological samples during human pharmacokinetic studies. The laboratory will develop and validate a specific analytical procedure via LC tandem mass spectrometry by triple quadrupole. The method is able to detect the three analytes at once, namely levofloxacin, dexamethasone and dexamethasone 21-phosphate. This method will allow a minimum quantity of aqueous humour (i.e. 50 μ l) to be withdrawn from each patient. The vials containing frozen aqueous humour will contain no information regarding the drug received. Quality control samples blinded to the analyst will be included following advice from BfArM. To that end, the randomization list will include kit numbers corresponding to quality control samples. Twelve samples will be prepared with synthetic aqueous humour and a known concentration of the active ingredients in pre-labelled vials at the central laboratory by a different analyst in presence of OPIS personnel. The twelve quality control samples correspond to 10% of the true biological samples obtained from the patients.

The laboratory analyst will thus be blinded to the drug administered and samples will be analysed for the concentration of all three molecules (levofloxacin, dexamethasone 21-phosphate and dexamethasone). All the analyses will be done in a single run and will not be duplicated.

Further details are provided in the laboratory protocol (*Appendix 1*).

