10.1.7 QUALITY ASSURANCE AND QUALITY CONTROL

Following written Standard Operating Procedures (SOPs), monitors will verify that the clinical trial is conducted and data are generated, documented (recorded), and reported in compliance with the protocol, International Conference on Harmonisation Good Clinical Practice (ICH GCP), GLP and applicable regulatory requirements.

The investigational site and central laboratory will provide direct access to all trial-related facilities, source data/documents, and reports for the purpose of monitoring and auditing by the sponsor, and inspection by local and regulatory authorities.

Independent audits may be conducted to ensure monitoring practices are performed consistently across all participating sites and that monitors are following the MP. Independent audits may be conducted by the Sponsor to ensure monitoring practices are performed consistently across all participating sites and that monitors are following the MP.

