3 DATA PROCESSING

All the data are processed using Analyst software version 1.6.2 associated with the mass spectrometer. Calibration curves are constructed by plotting the peak area ratio of Levofloxacin, Dexamethasone 21-phosphate and Dexamethasone to IS against the theoretical concentration of the analytes.

The concentration values in the study samples are directly calculated by the software using an optimal calibration curve defined during the method validation. Integration will be performed by the software or manually by the operator if the peak shape is anomalous or if the baseline is noisy. The manual integration is reported on the summary table elaborated by the software in the column "record modified", according to the TicinumLab SOP GCP004.

Code: GCLP022/01

Page. 18 of 27

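### Does the three-analyte read-out undo the laboratory analyst's blinding, so that manual peak integration needs a further rule?

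*Combined protocol and SAP*

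**What the plan says.** Vials carry a kit number and nothing about treatment (protocol 4.1, 6.3, 8.2). Section 4.1 states: "The laboratory analyst will be blinded to the drug administered and samples will be analysed for the concentration of all three molecules". Section 8.2 adds: "The method is able to detect the three analytes at once, namely levofloxacin, dexamethasone and dexamethasone 21-phosphate". Section 4.2 gives the purpose: "The laboratory analyst will be blinded to the drug administered to ensure an unbiased analysis".

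A second safeguard follows in 4.1: "Quality control samples blinded to the analyst will be included following advice from BfArM". Section 6.3 gives their number and make-up: "Twelve samples (4 of each active principle) will be prepared with synthetic aqueous humour". A different analyst prepares them, with CRO staff present, and they take kit numbers from the randomization list.

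On reading the chromatograms, section 3 (Data Processing) of the laboratory protocol in Appendix 12.1 says: "Integration will be performed by the software or manually by the operator if the peak shape is anomalous or if the baseline is noisy". On traceability it says: "The manual integration is reported on the summary table elaborated by the software in the column" for modified records, and it cites a laboratory SOP that is not reproduced. Under the same section the software calculates concentrations from the peak-area ratio to the internal standard, using a calibration curve defined during validation. Protocol 10.1.7 provides for audit: "The investigational site and central laboratory will provide direct access to all trial-related facilities, source data/documents, and reports".

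**The concern.** Masked labels hide the arm during handling, preparation and injection. At read-out the picture changes. A sample with levofloxacin and steroid suggests the combination, levofloxacin alone suggests the levofloxacin arm, and steroid alone suggests the dexamethasone arm. Section 5.2 excludes other topical and systemic steroids and antibiotics for 7 days before surgery, so no permitted medicine blurs the pattern.

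Manual integration is the one visible judgement between the instrument and the endpoint. If the operator can see all channels, knowledge of the arm could in principle affect which peaks are redrawn and how. The analyst is the only role the protocol describes as blinded, samples are not assayed in duplicate (8.2), and the concentrations go straight into the summaries by arm (9.4.2). What is at stake is the fairness of setting combination beside single drug, and whether the claim in 4.2 holds at this last step.

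**Working it through.** **1. The plan's own figures.** Section 9.2 uses half-width = 1.96 × SD / √40.
- Dexamethasone: 1.96 × 15 / √40 = 4.648 ng/ml, as stated.
- Levofloxacin: 1.96 × 199.022 / √40 = 61.676 ng/ml, as stated.
- Quality-control share: 12/120 = 10%, as stated in 4.1.

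**2. Lowest calibration standard (level G, laboratory protocol 2.4.1; molecular weights in 1.7.1).**
- Dexamethasone: 0.0127 nmol/ml × 392.46 = 5.0 ng/ml.
- Levofloxacin: 0.0138 nmol/ml × 361.37 = 5.0 ng/ml.

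**3. How far does the pattern reveal the arm?** The documents give an SD but no expected mean. I assume lognormal dexamethasone with SD 15 and mean m, and levofloxacin quantifiable in every eye that received it. With σ² = ln(1 + (15/m)²) and μ = ln m − σ²/2, the share of steroid-dosed samples below 5 ng/ml is f = Φ((ln 5 − μ)/σ).

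| Assumed mean m (ng/ml) | f | Correct guesses, (80 + 40(1−f))/120 | Pattern possible in one patient arm only, (40 + 40(1−f))/120 | Chance that a levofloxacin-only patient sample is from the levofloxacin arm, 40/(40 + 40f) |
|---|---|---|---|---|
| 5 | 0.776 | 74.1% | 40.8% | 56.3% |
| 10 | 0.462 | 84.6% | 51.3% | 68.4% |
| 15 | 0.183 | 93.9% | 60.6% | 84.5% |
| 20 | 0.041 | 98.6% | 65.3% | 96.1% |
| 30 | 0.0002 | 100.0% | 66.7% | 100.0% |

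The third column should not be read as the share of samples whose arm is revealed. Its floor is 80/120 = 67%: calling every levofloxacin-positive sample the levofloxacin arm scores that much even if no steroid is ever seen. The last two columns belong together. At low means the levofloxacin-only pattern is ambiguous; at means of 20 to 30 ng/ml the read-out shows the arm almost completely.

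**4. What the quality-control vials add.** The make-up of the vials can be read in two ways.
- One active per vial: a levofloxacin-only vial is a levofloxacin-arm patient with probability 40/(44 + 40f), which is 53.3% to 90.9%. A steroid-only vial is a dexamethasone-arm patient with probability 40(1−f)/(40(1−f) + 8), which is 52.8% to 83.3%.
- All actives in every vial: a both-drugs vial is a combination patient with probability 40(1−f)/(40(1−f) + 12), which is 42.7% to 76.9%.

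So some vials of known content look like patient samples. An operator who edited by pattern would risk editing these too, and the error would show against the known value. Cover is incomplete: on the first reading no vial resembles the combination arm, on the second none resembles a single-drug arm, and 12 vials give little power.

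**5. Size needed to matter.** Moving a 40-patient dexamethasone mean by one half-width takes edits summing to 40 × 4.648 = 186 ng/ml, all in one direction. The documents give no edit rate. For an assumed 4 to 12 edits, that is 186/4 = 46.5 down to 186/12 = 15.5 ng/ml each, or 3.1 to 1.0 SD. For levofloxacin, 40 × 61.676 = 2,467 ng/ml, or 617 to 206 ng/ml each, again 3.1 to 1.0 SD.

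Conversely, suppose each edit moved a value by 5 ng/ml, the size of the lowest standard. The mean would shift by 4 × 5/40 = 0.5 to 12 × 5/40 = 1.5 ng/ml, which is 11% to 32% of the half-width, and only if every edit went the same way.

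**The case for a change.** The strongest case for a change is that the remedy is cheap and aimed at the right place. Reviewing one analyte at a time would hide exactly the contrast of interest, combination against single drug. Fixing the integration settings before the run and listing automatic beside manual values would need no extra sample. The log and the audit access make an edit traceable afterwards but do not keep the decision to edit independent of the arm. With no duplicates, a doubtful edit has no replicate to expose it.

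Part of this stands. The read-out can point to the arm, the visible text is silent on what the operator may view, and 4.2 is worded more broadly than masked labels alone can deliver.

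The rest does not carry a change. The missing rule cannot be shown to be missing: section 3 refers manual integration to an SOP, the natural place for it, and the appendix is mainly a method-validation protocol. The quality-control vials are not powerless, as step 4 shows. Some visibility at read-out is also inherent in an assay of the molecules that define the arms. Nobody has established that the software can hide channels, so the main remedy may not be available.

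**Conclusion.** No change to the plan follows. This is missing detail with no demonstrated gain from adding it. Followed as written, the plan still gives sound descriptive concentrations: the software integrates unless a peak is anomalous or the baseline noisy, edits are logged, source data are open to audit, and blinded vials of known content are mixed in with the patient samples. Section 9.1 sets no hypothesis and plans no inferential analysis, so no test or margin could be tipped by a small shift.

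On the assumptions above, a shift as large as the planned half-width would need one-directional edits of 1.0 to 3.1 SD in each of 4 to 12 samples. Edits of about the lowest standard would move the dexamethasone mean by at most about a third of the half-width. These figures rest on an assumed number and size of edits, and step 3 rests on assumed means and a lognormal shape. The true size and direction of any bias cannot be computed from the documents. Confidence is moderate, because the SOP has not been seen.
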